### **8.1.3 Echocardiography**

If routinely conducted, following echocardiography parameters will be collected : systolic pulmonary arterial pressure (sPAP), Tei-Index, right atrial and ventricular area, tricuspid annular plane systolic excursion (TAPSE), right and left ventricular pump function will be assessed.

### **8.1.4 Determination of WHO functional class**

As part of the routine, functional assessment of pulmonary hypertension is performed according to the WHO-Functional Class, i.e. the Evian Symposium, 1998, modified New York Heart Association (NYHA) Classification:

Class I: Patients with PH but without resulting limitation of physical activity. Ordinary physical activity does not cause undue dyspnoea or fatigue, chest pain or near syncope.

Class II: Patients with PH resulting in slight limitation of physical activity. They are comfortable at rest. Ordinary physical activity causes undue dyspnoea or fatigue, chest pain or near syncope.

Class III: Patients with PH resulting in marked limitation of physical activity. They are comfortable at rest. Less than ordinary activity causes undue dyspnoea or fatigue, chest pain or near syncope.

Class IV: Patients with pulmonary hypertension with inability to carry out any physical activity without symptoms. These patients manifest signs of right heart failure. Dyspnoea and/or fatigue may even be present at rest. Discomfort is increased by any physical activity.

### **8.1.5 Lung function tests and blood gas analysis**

As available and per clinical practice visit schedule following parameters will be collected:

Lung function test: Body plethysmography (preferred method) including forced vital capacity (FVC), forced expiratory volume in one second (FEV1), forced expiratory flow (FEV), total lung capacity (TLC), diffusion-limited carbon monoxide (DLCo), residual volume), normally accounting for about 25% of TLC.

Blood gas analysis: capillary or arterial blood gas analysis; partial pressure of oxygen and carbon dioxide, oxygen saturation, supplemental oxygen “yes” or “no” (if the patient receives supplemental oxygen the amount will be recorded in the CRF in liters/minute).

### **8.1.6 6-minute walking distance and Borg dyspnea Score (CR 10)**

As part of clinical practice visits patient is asked to walk along a prescribed path as far as possible during a 6 minute interval of time. The patient may walk at whatever pace he/she feels comfortable with the goal of walking the most distance he/she feels possible. If the patient feels the need to rest, he/she may do this. Blood pressure, heart rate and oxygen saturation are measured before and after the test. The Borg Scale (Breathlessness Scale) is commonly used to measure shortness of breath of patients or in sports medicine.

The Borg Scale comprises the following parameters according to the ATS guidelines (ATS 2002):

0	Nothing at All
0.5	Very very slight (just noticeable)
1	Very slight
2	Slight
3	Moderate
4	Somewhat Moderate
5	Severe
6	
7	Very Severe
8	
9	Very very severe (almost maximal)
10	Maximal

### **8.1.7 Quality of Life (QoL):**

QoL will be assessed as part of clinical practice visits using the SF 36-questionnaire (see Appendix) that will be handed out to the patients. Scoring will be carried out according to the test manual.

The SF-36 consists of eight scaled scores, which are the weighted sums of the questions in their section. Each scale is directly transformed into a 0-100 scale, i.e. a score of zero is equivalent to maximum disability and a score of 100 is equivalent to no disability. The eight sections are: vitality; physical functioning; bodily pain; general health perceptions; physical role functioning; emotional role functioning; social role functioning; mental health.

### 8.1.8 Vital signs

Blood pressure, heart rate and oxygen saturation will be recorded according to current clinical practice.

### 8.1.9 Electrocardiography

If performed as part of clinical practice visits, data from a 12-lead electrocardiogram (ECG) will be reviewed for potential AEs.

A continuous 3-lead ECG monitoring will be applied during right heart catheterization.

### 8.1.10 Clinical laboratory data

As available and determined locally on-site, following clinical laboratory data will be collected:

Hematology	Leucocytes, erythrocytes, hemoglobin, hematocrit, platelets
Substrates	Bilirubin, LDL/HDL, cholesterol, triglycerides, creatinine, uric acid, urea, total protein, albumin, glucose
Electrolytes	Sodium, potassium, calcium, chloride
Enzymes	SGOT/ASAT, SGPT/ALAT, Gamma-GT, GLDH, AP, LDH, CK
Others	INR, PTT, $\beta$ -HCG test for women with childbearing potential at initial screening, Visit 3 and Visit 4
Biomarkers	CRP, NT-proBNP

## 8.2 Data Collection Schedule

Patients will be assessed according to routine clinical examinations in their respective pulmonary hypertension expert center. According to the current guidelines, patients will be seen in the expert center about every three months. This will allow to collect data within the first 6 months of treatment and compare changes between initiation of new i.v. epoprostenol (Veletri®) therapy, after 3 and 6 months (~24 weeks).

Routine medical examinations comprise of medical history, physical examination, electrocardiogram (ECG), laboratory testing (including NT-proBNP), echocardiography at rest, and right heart catheterization according to clinical practice of the PH center. If patients fulfill the inclusion criteria they will be invited to join this non-interventional trial. The prospective period of data collection will comprise of a ~24-week observation period and a follow-up phase of about  $30 \pm 7$  days.

No additional assessments will be performed due to the study. All decisions regarding treatment and titration of i.v. epoprostenol (Veletri®) are based on the treating physicians decision.

Table 1 provides an overview of the variables collected at initiation of i.v. epoprostenol (Veletri®) therapy and/or during the observation period (follow-up visits), if available, per clinical practice.

**Table 1: CRF data collection (as available per clinical practice from the existing medical record)**

Variable / Clinical characteristics	Initiation of i.v. epoprostenol (Veletri®) therapy	Follow-up (at any clinical practice visit)
Informed consent	X	
Medical History	X	
Inclusion/Exclusion Criteria Review	X	
Demographics (age, gender, country)	X	
Physical examination and vital signs	X	X
WHO classification	X	X
Electrocardiogram - ECG	X	X
Echocardiography at rest	X	X
Right heart catheterization	X	X
6MWD-test	X	X
(Lung function test	X	X
Patient Questionnaire 1 (QoL)	X	X
Patient Questionnaire 2 (Borg dispnoe score)	X	X
Lab tests/assay 1 (including NT-proBNP)	X	X
Lab tests/assay 2 (Pregnancy test)	X	

## 9 Adverse Events

### 9.1 Definitions

#### 9.1.1 Adverse Event

According to Good Clinical Practice GCP, an adverse event (AE) is defined as follows: Any untoward medical occurrence in a subject administered a pharmaceutical product and which does not necessarily have a causal relationship with this treatment. An AE can therefore be any unfavorable and unintended sign (including an abnormal laboratory finding), symptom, or disease temporally associated with the use of a medicinal product, whether or not related to the IMP.

An AE may be:

- New symptoms/ medical conditions

- New diagnosis
- Significant changes of laboratory parameters
- Intercurrent diseases and accidents
- Worsening (change in nature, severity or frequency) of medical conditions/ diseases existing before trial start
- Recurrence of disease
- Increase of frequency or intensity of episodic diseases.
- Events related or possibly related to concomitant medications

A pre-existing disease or symptom will not be considered an adverse event unless there will be an untoward change in its intensity, frequency or quality. This change will be documented by an investigator.

Surgical procedures themselves are not AEs; they are therapeutic measures for conditions that require surgery. The condition for which the surgery is required may be an AE. Planned surgical measures permitted by the trial protocol and the condition(s) leading to these measures are not AEs, if the condition leading to the measure was present prior to inclusion into the trial.

AEs are classified as "non-serious" or "serious".

### **9.1.2 Serious Adverse Event**

A serious adverse event (SAE) is one that at any dose:

- Results in death
- Is life-threatening (the term life-threatening refers to an event in which the subject was at risk of death at the time of event and not to an event which hypothetically might have caused death if it was more severe)
- Requires subject hospitalization or prolongation of existing hospitalization (unless the admission results in a stay of less than 12 hours or the admission is pre-planned or the admission is not associated with an adverse event)
- Results in persistent or significant disability/ incapacity or
- Is a congenital anomaly/ birth defect.
- Medical and scientific judgment should be exercised in deciding whether expedited reporting is appropriate in other situations, such as important medical events that may not be immediately life-threatening or result in death or hospitalization but may jeopardize the patient or may require intervention to prevent one of the other outcomes listed in the definition above. These should also usually be considered serious (e.g. treatment at home for allergic bronchospasm).

### 9.1.3 Expectedness

An ‘unexpected’ adverse event is one the nature or severity of which is not consistent with the applicable “Summary of Product Characteristics” (SmPC) or scientific literature. Furthermore, reports which add significant information on specificity or severity of a known adverse reaction constitute ‘unexpected’ events.

### 9.1.4 Suspected Unexpected Serious Adverse Reaction (SUSAR)

SAEs that are both suspected, i.e. possibly related to IMP and ‘unexpected’, i.e. the nature and/or severity of which is not consistent with the applicable product information are to be classified as Suspected Unexpected Serious Adverse Reactions (SUSARs). The definition covers also medication errors and uses outside what is foreseen in the protocol, including misuse and abuse of the product.

In case, either the investigator who primarily reported the SAE or the second assessor classify the SAE as ‘suspected’ (i.e. either definitely or *probable* or *possible related* to the IMP or *not assessable*) and the SAE is unexpected it will be categorized as a SUSAR.

All SUSARs are subject to an expedited reporting to the responsible ethics committee(s), the competent higher federal authority, i.e. Bundesinstitut für Arzneimittel und Medizinprodukte (BfArM), and to all participating investigators.

### 9.1.5 Grading of AEs

The **grading** of an AE should be assessed by the investigator according to the 5-grade scale defined in the Common Terminology Criteria for Adverse Events (CTCAE) v4.03 established by the National Cancer Institute (NCI) of the United States of America (USA) as follows:

- Grade 1: mild AE, temporary event which is tolerated well by the subject
- Grade 2: moderate AE; event which results in discomfort for the subject and impairs his/her normal activity
- Grade 3: severe AE; event which results in substantial impairment of normal activities of subject
- Grade 4: life-threatening AE or AE causing disablement
- Grade 5: death related to AE

### 9.1.6 Relationship and outcome of AEs, action taken

Each AE must be assessed by the investigator as to whether or not there is a reasonable possibility of causal relationship to the observed medicinal product (Veletri®) that was ongoing at the time of AE onset, and reported as either related or unrelated. The determination of the likelihood that the observed medicinal product (Veletri®) caused the AE shall be provided by an investigator who is a qualified physician.

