##### **4.1 Study population**

In this open label, multicenter non-interventional, observational study patients with PAH will receive medically indicated i.v. epoprostenol (Veletri®) according to a systematic drug management including initiation, administration, storage, handling of the infusion system and patient education. Patients in need of treatment escalation according to the current guidelines receiving at least dual oral combination treatment with two PAH-targeted drugs and having an unsatisfying long-term clinical response or are still in an intermediate or high risk group will be eligible for the study.

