## 7.2 Therapeutic Effects

Chronic pulmonary hypertension (PH) is associated with impaired exercise capacity, quality of life and right ventricular function.[1] The disease is characterized by an increase of pulmonary vascular resistance and pulmonary arterial pressure, leading to right heart insufficiency.[1, 2] Within the last decade, new disease-targeted medical therapies have been approved for treatment of pulmonary arterial hypertension (PAH).[3] Combinations of these agents have shown to further improve symptoms, 6-minute walking distance (6-MWD) and hemodynamics in PAH patients.[1, 3]

The loss of endogenous prostacyclin plays an important role in the pathogenesis of PAH. Prostacyclin has vasodilatory, anti-proliferative, anti-inflammatory and anti-thrombotic properties and is therefore an important target substance in PAH-specific therapy.[4] Epoprostenol was the first specific therapy approved for the treatment of PAH, after showing a positive effect on survival in otherwise treatment naïve patients.[5] Epoprostenol is chemically unstable with a short biological half-life of 3-5 minutes, and must be continuously administered by intravenous (i.v.) infusion using an external pump and in-dwelling central venous catheter.

The application of epoprostenol is therefore aggravated by its handling, which makes it a challenge for the patient to store and administer the medication.

Flolan® was the first epoprostenol drug that was made available for treatment of pulmonary arterial hypertension. Reconstituted flolan solution is stable at 2 - 8 °C for up to 48 hours. If used immediately, reconstituted flolan is stable for up to 12 hours at room temperature (< 25 °C), or prior to use at room temperature, reconstituted flolan may be stored at 2 - 8 °C for up to 40 hours. In this case, flolan should not be infused for over 8 hours at room temperature.

With Veletri® an improved epoprostenol solution has been therefore developed to facilitate storage and administration of the drug. It provides a better stability upon reconstitution is self-preserving, does not allow the growth of micro-organisms and allows reconstitution with readily available diluents.

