#### **7.4 Dosage Schedule, Titration and Administration**

This non-interventional trial aims to investigate the use and titration of i.v. epoprostenol (Veletri®) in clinical practice. To guide physicians during the titration phase, the following informations will be provided, allowing a systematic approach to dosing. Informations given to the study phasicians include initiation, titration, dosage, known side effects and administration. This information is however not binding, but shall help the treating physician to handle i.v. administration of i.v. epoprostenol (Veletri®).

Official dosage recommendations are as follows:

- Initiation of chronic infusion of i.v. epoprostenol (Veletri®) at 2 ng/kg/min (or lower if not tolerated)
- Increase in increments of 2 ng/kg/min every 15 minutes or longer until a tolerance limit to the drug is established or further increases in the infusion rate are not clinically warranted.
- Decrease of dosage if dose-limiting pharmacologic effects occur
- In clinical trials, the most common dose-limiting adverse events were nausea, vomiting, hypotension, sepsis, headache, abdominal pain, or respiratory disorder (most treatment-limiting adverse events were not serious).

In the controlled 12-week trial in PAH/SSD, for example, the dose increased from a mean starting dose of 2.2 ng/kg/min. During the first 7 days of treatment, the dose was increased daily to a mean dose of 4.1 ng/kg/min on day 7 of treatment. At the end of week 12, the mean dose was 11.2 ng/kg/min. The mean incremental increase was 2 to 3 ng/kg/min every 3 weeks.

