### **Administration**

Veletri, once prepared as directed, is administered by continuous intravenous infusion via a central venous catheter using an ambulatory infusion pump. During initiation of treatment, i.v. epoprostenol (Veletri®) may be administered peripherally.

Infusion sets with an in-line 0.22 micron filter should be used.

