## 9.2 Period of Observation and Documentation

All AEs reported by the patient or detected by the treating physician / investigator, are routinely being documented in the subject's medical records. For the purpose of this observational trial all AEs that occur after the initiation of i.v. epoprostenol (Veletri®) up to the last visit will also be documented on the pages provided in the CRF. AEs will be assessed by the investigator using no-leading questions or observed during any visit during the whole observation. The patient should be motivated to report any AEs by phone to the investigator occurring between clinical visits.

Each event should be described in detail along with start and stop dates, severity, relationship to the observed product, action taken and outcome.

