#### **Primary endpoint**

The main parameters are safety and tolerability parameters of i.v. epoprostenol (Veletri®). Data regarding safety and tolerability will be collected by listings of adverse reactions during the course of the medically indicated treatment.

**Secondary efficacy variables** will be formally tested for statistical significance of a difference between baseline and 3 months; baseline and 6 months, respectively.

Secondary efficacy analysis comprises hemodynamics, echocardiography, lung function tests, 6MWD, Borg Dyspnea index, Modified Rodnan Skin Score, laboratory parameters, quality of life and safety parameters.

WHO functional class is supposed to either remain the same, improve by one or two categories, or deteriorate by one category in most cases. A change score (baseline minus end of study) will be calculated, which could go from -3 (class 4 at baseline and class 1 at end of study) to +1 (class 3 at baseline and class 4 at end of study). This will be analyzed using the Wilcoxon test.

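### Causality is asked for the drug only, so catheter, pump and preparation harms have no attribution category in a study of infusion management

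*Protocol*

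**What the plan says.** **What is studied.** Section 3.1 sets out to explore the use, safety and tolerability of a structured way of managing intravenous epoprostenol. Sections 4.1 and 10.3 describe it as "systematic drug management including initiation, administration, storage, handling of the infusion system and patient education". Under section 7.4 (Administration) the product is "administered by continuous intravenous infusion via a central venous catheter using an ambulatory infusion pump", although the start of treatment may use a peripheral line.

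**How causality is recorded.** Section 9.1.6 asks for one judgement per event, on a reasonable possibility of a "causal relationship to the observed medicinal product (Veletri®) that was ongoing at the time of AE onset, and reported as either related or unrelated". Section 9.2 requires each event to be described with "start and stop dates, severity, relationship to the observed product, action taken and outcome". The AE/ADR form in section 9.3 also asks for relationship to the medicinal product and to nothing else.

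**When recording starts.** Section 9.2 covers "all AEs that occur after the initiation of i.v. epoprostenol (Veletri®) up to the last visit".

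**What the primary analysis contains.** Section 3.1 (and the Protocol Outline) names three listings: Veletri-associated adverse drug reactions, SAEs, and AEs during therapy. The primary-endpoint paragraph of section 10.4.1 says: "Data regarding safety and tolerability will be collected by listings of adverse reactions during the course of the medically indicated treatment". The safety paragraph of the same section promises tables of AEs and SAEs.

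**The concern.** Infusion through a catheter and pump can cause harm that is not pharmacological: line infection or thrombosis, dislodgement, pump failure, errors in preparing the cassette, unplanned interruption. A structured management programme that covers handling of the system and patient education bears directly on such events, so they belong to the study's own question.

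The planned record cannot answer that part. With one causality target and two answers, a pump failure has to be rated as related or unrelated to a drug. One investigator may choose related, because the event arose from giving the drug. Another may choose unrelated, because the drug substance did not cause it. The first rating puts the event among the Veletri-associated reactions and the second leaves it out. In neither case does the record show that the delivery system was the cause.

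Two consequences follow. The ADR frequency mixes drug and delivery harms in a proportion set by individual reading of the form, pooled over centres and only about 15 patients. And the study has no defined count of delivery harms, the figure most informative about management of the infusion. An analysis plan cannot restore an attribution that was not collected.

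**Working it through.** The protocol states no figure on this point, and the sample of about 15 comes without a calculation, so there is nothing to reproduce. The check is of the text, with arithmetic for scale.

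**1. Object of study against object of attribution**

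| Item | Section | Covers the delivery system? |
|---|---|---|
| Management under study | 4.1, 10.3 | Yes: administration, storage, handling of the infusion system |
| Causality judgement | 9.1.6 | No: Veletri only, two categories |
| Per-event description | 9.2 | No: product only |
| AE/ADR form | 9.3 | No: product only |

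None of the three recording points has a category for catheter, insertion, pump, preparation or interruption.

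**2. Where a delivery event after initiation would appear**

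| Listing or table | If rated related | If rated unrelated |
|---|---|---|
| ADR listing (3.1) | Yes | No |
| SAE listing (3.1), if serious | Yes | Yes |
| AE listing (3.1) | Yes | Yes |
| Primary-endpoint paragraph (10.4.1) as worded | Yes | No |
| AE and SAE tables (10.4.1, Safety analysis) | Yes | Yes, SAE table if serious |

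The rating decides two rows: the ADR listing, and the primary analysis as 10.4.1 words it. The second exists only because 10.4.1 is narrower than 3.1.

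**3. Recording window.** Recording starts at initiation of the drug. Because initiation may be peripheral, the central line may be placed before or after that moment. Insertion harm is recorded in the second case. In the first, section 9.2 does not call for it.

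**4. Scale.** The protocol gives no rate of delivery events, so the rates p and counts x below are assumptions, with n = 15.

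Expected number of patients affected = 15p; chance of at least one = 1 − (1 − p)^15.

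- p = 5%: 0.75 expected; 1 − 0.95^15 = 53.7%
- p = 10%: 1.5 expected; 1 − 0.90^15 = 79.4%
- p = 20%: 3.0 expected; 1 − 0.80^15 = 96.5%

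Observed frequency x/15 with exact (Clopper-Pearson) 95% limits:

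- x = 1: 6.7% (0.2 to 31.9)
- x = 2: 13.3% (1.7 to 40.5)
- x = 3: 20.0% (4.3 to 48.1)

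If x patients have a delivery event, the number who enter the ADR listing on that account may be anything from 0 to x, depending on the ratings. At the extreme of 0/15 the exact upper limit is 1 − 0.025^(1/15) = 21.8%. These figures show that the question will probably arise at least once. They do not estimate a bias.

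**The case against.** A reader might infer that delivery harms will be scored as unrelated. No section requires that. The threshold in 9.1.6 is only a reasonable possibility. Section 7.4 reports that in clinical trials "the most common dose-limiting adverse events were nausea, vomiting, hypotension, sepsis, headache, abdominal pain, or respiratory disorder", which points towards related for line sepsis. Section 9.1.4 brings medication errors within its definition of suspected unexpected serious reactions, which could take in some serious preparation errors. So the rating is undefined, not fixed at unrelated.

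A reader might also infer that such events vanish from the primary result and bias it downwards. Section 3.1 does not support that: SAEs and all AEs are primary listings alongside ADRs, neither depends on causality, and 10.4.1 tabulates both. A line infection leading to hospitalisation would normally qualify as an SAE under 9.1.2 whatever its rating.

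A third tempting reading is that 7.3 contradicts 7.4 by omitting sepsis. The two lists differ in kind: 7.3 gives side effects by frequency or by difference between groups, 7.4 gives dose-limiting events. The statement in 7.2 that the product "is self-preserving, does not allow the growth of micro-organisms" describes the solution and is not causality guidance.

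Finally, the form already asks for the nature of the event and the final diagnosis, so with about 15 patients many delivery events could be picked out by hand. That is fair, but it would be a retrospective judgement from free text, without the view of the physician who saw the event. A diagnosis such as sepsis or thrombosis does not say whether the line was the source.

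The first three arguments stand and limit the point. The last reduces the loss but does not remove it.

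**Conclusion.** The point holds in a limited form. Causality is collected for the drug alone, while the management under study includes handling the infusion system. Attribution of delivery harms is therefore left to each investigator, and drug reactions cannot be separated from delivery harms as planned. The effect is confined to the ADR component and to the primary-endpoint paragraph of 10.4.1, whose wording is narrower than section 3.1. Insertion harm before the first infusion is a further gap, but only where the line is placed first.

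The number of events affected is unknown, from none to all delivery events, because the protocol gives no rate and no rating rule. This conclusion assumes that the CRF pages, which are not at hand, follow 9.2 and 9.3. It is a cheap and worthwhile improvement; the documents do not show a primary result that is biased in a known direction.

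**What to change.** - **Sections 9.1.6, 9.2 and the form in 9.3:** record relationship separately for (a) the drug and (b) the delivery system, its insertion or its handling, including preparation and interruption. Allow both or neither.
- **Section 10.4.1, Primary endpoint:** align with section 3.1 so that the primary listing covers ADRs, SAEs and all AEs.
- **Presentation:** show these listings by attribution, with delivery-related events as their own row. Redefining the primary frequency as drug and delivery events combined is possible but is a choice, and this correction does not need it.
- **Section 9.2:** record delivery-related events from catheter placement when that precedes the first infusion and follows consent.

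The cost is one extra item on the form and one extra table row. No assessment is added and clinical management is untouched, so the change fits the non-interventional design. The reported treatment-associated frequency may come out slightly higher.
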